7.8 Interim Analyses

No interim analyses were planned for this cohort.

Descriptive summaries of the study data may be conducted as deemed appropriate throughout the study. All efforts will be made to ensure such descriptive analyses will not jeopardize the study final report.

In June 2021, Medtronic decided to halt the production and sale of the HVAD. In agreement with the steering committee (SC), it was decided to continue the Apogee study through its one year follow up for all enrolled and implanted patients. A final clinical study report will be created and shared with institutional review boards (IRBs) and sites, as applicable.

7.9 Evaluation of Objectives

Many ancillary objectives are not statistical in nature and since this is an observational study no hypothesis tests are planned.

The Apogee study might observe variations in data collection due to 1) variations in routine care practices across participating sites and 2) the COVID-19 pandemic. Apogee does not have statistical hypotheses; thus, available data will be analyzed.

If any of the analysis does not have enough data to provide a summary, metrics for completion and expected values will be provided in its place.

7.9.1 Primary Objective

To characterize the 12-month overall major AE rate after the collective impact of Apogee standardized protocols and best practices. Major AEs are defined to be occurrence of infection, bleeding, device malfunction, stroke death.

Events counted as “major adverse events” are:

- Major infection as defined by Intermacs adverse events V5
- Major bleeding as device by Adverse Events
- Device Malfunction as defined by Adverse Events
- Any stroke (includes both ischemic stroke, acute symptomatic ICH, and clinically covert ischemic stroke or ICH) as defined by Adverse Events as a sub-category of neurological dysfunction
- All-cause death

Time to first major adverse event will be analyzed using Kaplan-Meier methods, with Time 0 being exit from the operating room following implant. Patients will be censored upon the earliest of explant of the original device (e.g., transplant, recovery, exchange), study exit, Apogee withdrawal, last known follow-up, and the date of their 12-month follow-up (365 days will be used if 12-month follow-up was not completed and greater than 365 days was completed). Patients who have the device turned off, but not removed will continue to be followed the same as those patients who still have the device implanted and turned on. Patients who have devices repositioned will continue to be followed as per the regular follow up schedule. Failure time is the time to a primary objective

event. There is no planned formal comparison of the major AE rate, though it could be informally compared to results from other studies, or non-Apogee patients in DT PAS.

The number of patients left, survival rate and exact 95% confidence intervals (CI) will be summarized for all patients. In addition, the number of patients who met a failure endpoint (first failure) from implant to the time interval as well as the reasons for censoring will be summarized.

Failure:

- Major Infection
- Major Bleeding
- Device Malfunction
- Stroke
- Death

Censored:

- Survival on original device – 12 month follow up, 365 days post implant, or last known follow up
- Exchange
- Explant for Transplant
- Explant for Recovery

A stroke is a neurological dysfunction event specified as an ischemic stroke, acute symptomatic ICH, or clinically covert ischemic stroke or ICH. These must be confirmed with computed tomography (CT).

Events where the “What is the relative time from the procedure” is recorded as “DURING PROCEDURE” will be excluded from the analysis.

7.9.5 Other Objectives

7.9.5.1 Overall Survival

Overall patient survival will be summarized descriptively with Kaplan-Meiercurves. Time is measured from the day of implant of the study device. A patient is censored if the patient is explanted (e.g. transplant or recovery), if the patient is exchanged to a non-HVAD, the study is terminated (either overall or at the patient's investigative site), the patient withdraws consent (either from Apogee or PSR), or the patient is otherwise lost to follow-up. Patients who have the device turned off, but not removed or the device repositioned will continue to be followed the same as those patients who still have the device implanted and turned on. Only follow up and events (deaths) while a patient participated in Apogee will be included (12 month follow up visit, 365 days post implant, exit from DT PAS or withdrawal from Apogee). Failure time is the time to death on device.

The number of patients left, survival rate and exact 95% confidence intervals (CI) will be summarized for all patients. In addition, the number of patients who met a failure endpoint from implant to the time interval as well as the reasons for censoring will be summarized.

Patients who withdraw (either from the PSR or from just the Apogee study), are lost to follow up, or otherwise do not have a 12 month follow up (or 365 days post implant), but do not have a qualifying failure event, will be censored as of their last known date in the study.

Code similar to below will be used:

```
ods listing close;
proc lifetest data=alldata plots=survival (nocensor) outsurv=output1
maxtime=12 method=km;
  time endptmonth*censor(0);
  label endptmonth = "Months";
  ods output productlimitestimates=rate;
run;
ods listing;
```

Only DT PAS patients successfully implanted with the HeartWare HVAD and enrolled in the Apogee study will be included in this analysis.

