7.4 Handling of Missing, Unused, and Spurious Data and Dropouts

Data entry error or non-reasonable values will be cleaned before data analysis. In the event of patient exit or withdrawal of consent, the patient's data collected prior to study exit will still be included in the final statistical analysis. The specific reasons for patient exit or withdrawal will be provided in detail in the study report.

All available data (i.e., not missing) will be included in the tabulations and applicable data listings to be analyzed as described in this plan. Missing data will not be imputed.

This study will use the survival analysis method for the primary objective. If a patient withdraws or prematurely exits the study and no failure criteria were met, the last known date the patient was alive on device (same type as originally received – would include follow-up post exchange to another HVAD) and actively participating in the study will be used for the censoring date in the Kaplan-Meier analysis.

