7.7.2 System Modification

In the event a system modification occurs, the data will be collected on the eCRFs. A system modification occurs when the pump is removed from the body and not replaced (e.g., heart transplant, explant for recovery), the pump is removed from the body and is replaced by another HVAD or other mechanical support device (i.e., exchange), if the pump is turned off but not removed from the body (e.g., for recovery, hospice/end of life), or if the pump needs to be repositioned. A summary of the number of patients with a system modification and total number of system modifications will be provided, breaking out the reason for system modification. A separate table will further subclassify the new device received for exchanges and the reason for a heart transplant. Only events while a patient participated in Apogee will be included (12 month follow up visit, 365 days post implant, withdrawal from Apogee, or exit from DT PAS).

Note that any system modifications after 03-Jun-2021 which result in an exchange should be to a non-HVAD device, given the stop of implants of the HVAD.

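### The SAP's 'overall survival' curve estimates survival on HVAD support with device removal censored, and should be named and supplemented accordingly

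*SAP*

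**What the plan says.** SAP 7.9.5.1 opens with "Overall patient survival will be summarized descriptively" by Kaplan-Meier, with time measured from the day of implant. The failure definition is narrower: "Failure time is the time to death on device". The first censoring events are set out as follows: "A patient is censored if the patient is explanted (e.g. transplant or recovery), if the patient is exchanged to a non-HVAD". Study termination, withdrawal and loss to follow-up also censor. A pump that is switched off or repositioned but left in place does not.

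Exchange to another HVAD is not among the censoring events. SAP 7.4, writing about the primary objective, describes the device concerned as "same type as originally received – would include follow-up post exchange to another HVAD".

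Two other sections bear on how this works in practice. SAP 7.7.2 notes that "any system modifications after 03-Jun-2021 which result in an exchange should be to a non-HVAD device, given the stop of implants of the HVAD". SAP 7.8 says that after the June 2021 halt "it was decided to continue the Apogee study through its one year follow up for all enrolled and implanted patients".

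The readable text contains no survival analysis that ignores device status and no competing-risks analysis. Parts of the SAP are redacted, so one there cannot be ruled out. It would not change what 7.9.5.1 estimates.

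**The concern.** The name promises one quantity and the rules produce another. A death within 12 months of implant, but after transplant, recovery explant or exchange to a non-HVAD, cannot count. Kaplan-Meier treats each censored patient as having, from then on, the same risk as those still on an HVAD. That is a strong assumption when the censoring event is itself a clinical turning point. Exchange may follow a device complication, while transplant or recovery may signal a better or a worse outlook.

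What is at stake is how the final report is read. SAP 7.9.1 already foresees informal comparison of the major adverse event rate with other studies and with non-Apogee DT PAS patients. A curve titled 'overall survival' invites the same comparison with all-cause figures, and the two would not be measuring the same thing.

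**Working it through.** **No stated figure to reproduce.** The SAP gives no survival rate, removal rate or event count for this analysis. The check is therefore a comparison of definitions, followed by an illustration on assumed rates.

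**1. Exchange rules side by side**

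| SAP section | Concerns | Effect of exchange to another HVAD | Effect of exchange to a non-HVAD |
|---|---|---|---|
| 5.5 | Data collection | Ends (any exchange) | Ends |
| 6 | Apogee follow-up | Continues | Ends |
| 7.4 | Censoring date, primary objective | Continues | Ends |
| 7.9.1 | Primary endpoint | Censored (any exchange) | Censored |
| 7.9.5.1 | Overall survival | Continues | Censored |
| 7.9.5.2 | Adverse event counting | Continues | Ends |

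Sections 6, 7.4, 7.9.5.1 and 7.9.5.2 agree with one another. Section 5.5 conflicts with them, because follow-up after an HVAD exchange needs data that 5.5 stops collecting. Sections 7.4 and 7.9.1 give different rules for the same endpoint.

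**2. Calendar time.** The rule in 7.9.5.1 depends on the type of replacement device and is the same throughout. From 7.7.2, exchanges after 03-Jun-2021 are expected to be to non-HVADs, and so to be censored. Before that date either outcome was possible. From 7.8, one-year follow-up was still running at the halt, so exchanges could fall on both sides of it. The documents do not say how many did.

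**3. Possible size of the gap**

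Inputs, all assumed:
- on-device 12-month survival S = 0.80
- probability of removal by 12 months, in the absence of death, p = 0.05, 0.10 or 0.15
- ratio of the death hazard after removal to that before, k = 0.25, 1, 3 or 5

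Hazards are constant and time is in years:
- h = -ln(0.80) = 0.2231
- c = -ln(1 - p) = 0.0513, 0.1054 or 0.1625
- the 7.9.5.1 curve at 12 months estimates exp(-h) = 0.80
- all-cause survival = exp(-(h + c)) + I
- I = integral from 0 to 1 of c·exp(-(h + c)u)·exp(-kh(1 - u)) du, which is the probability of being removed and still alive at 12 months

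For p = 0.15, exp(-(h + c)) = 0.80 × 0.85 = 0.68.
- With k = 5, I = 0.0784. All-cause survival is 0.7584 and the gap is 0.80 - 0.7584 = +4.2 points.
- With k = 0.25, I = 0.1309. All-cause survival is 0.8109 and the gap is 0.80 - 0.8109 = -1.1 points.

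Gap (curve minus all-cause survival, percentage points):

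| Removed by 12 months | k = 0.25 | k = 1 | k = 3 | k = 5 |
|---|---|---|---|---|
| 5% | -0.36 | 0 | +0.78 | +1.36 |
| 10% | -0.72 | 0 | +1.57 | +2.75 |
| 15% | -1.09 | 0 | +2.38 | +4.16 |

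A wider grid (S of 0.80 or 0.85, p from 0.03 to 0.15, k from 0.25 to 6) gives -1.1 to +4.9 points.

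**4. Scale against sampling error.** SAP 5.2 gives 124 co-enrolled patients. If all are analysed and none censored, the approximate 95% half-width at S = 0.80 is 1.96 × sqrt(0.80 × 0.20 / 124) = 7.0 points.

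**The case against.** The strongest reply is that nothing is hidden. Section 7.9.5.1 defines failure, lists each censoring event and requires the reasons for censoring to be summarised. Section 7.7.2 adds counts of system modifications by reason, the new device received at exchange and the reason for transplant. The analysis is descriptive, sits under other objectives and carries no hypothesis test. Following patients while they remain on an HVAD is coherent for an HVAD cohort. The gap may also be smaller than the sampling error. All of this stands, and it makes the point one of labelling and completeness rather than a flaw in the study's main result. It does not make the label right: disclosed censoring still leaves a curve that is not overall survival, and a table of censoring reasons does not show when patients left by each route.

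A reader might also infer three stronger things that the documents do not support.

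- *That the curve overstates survival.* This needs a higher risk of death after removal. Censoring covers transplant and recovery as well as exchange, and later risk may be lower in some of these groups. At a ratio of 0.25 the gap reverses, and no document fixes the direction.
- *That the estimand changes on 03-Jun-2021.* The rule is constant. Only the expected mix of replacement devices changes, and a non-HVAD exchange before that date was censored too.
- *That all exchanges should be treated alike.* A patient exchanged to another HVAD is still on HVAD support. Censoring that patient would contradict the proposed name and depart from sections 6, 7.4 and 7.9.5.2.

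**Conclusion.** The point holds as a mismatch between name and estimand. Followed exactly, SAP 7.9.5.1 yields survival on HVAD support with removal censored. Leaving aside chance offsetting between routes of removal, it matches overall survival only if removal is unrelated to the risk of death.

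On the assumed rates (20% on-device mortality, 5-15% removed, hazard ratio 0.25 to 5, constant hazards) the discrepancy is about -1.1 to +4.2 points, and 0 at a ratio of 1. The sign is unknown and the size is illustrative. Deaths left uncounted do not by themselves create a bias: at a ratio of 1 some deaths after removal are missed and the gap is still 0. What matters is whether risk after removal differs from risk on support.

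The primary endpoint is not affected by this label. The disagreement between 7.4 and 7.9.1 over HVAD-to-HVAD exchange does touch it and needs resolving in its own right.

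**What to change.** 1. Rename 7.9.5.1 and its outputs 'survival on HVAD support'. State that removal is censored, that HVAD-to-HVAD exchanges remain in follow-up, and that a pump switched off but left in place still counts as support.
2. Add Aalen-Johansen cumulative incidences to day 365 for four outcomes: death on HVAD support, transplant, explant for recovery, and exchange to a non-HVAD. Withdrawal and loss to follow-up stay censored. Section 7.7.2 already collects the modification types, reasons and replacement devices.
3. Use the term 'overall survival' only for an analysis from implant that also counts deaths after removal. Whether that is possible depends on what DT PAS follow-up records, and the DT PAS addendum was not available here. If vital status after removal is not recorded, say so and omit the term.
4. Reconcile the exchange rules in SAP 5.5, 6, 7.4, 7.9.1 and 7.9.5.1, so that data collection and censoring can be programmed without choosing between sections.

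Items 1, 2 and 4 cost SAP wording and one extra figure from data already planned. Item 3 needs vital-status data whose availability has to be confirmed first.

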7.9.5.2 Intermacs-Defined Adverse Events

All Intermacs V5-defined events will be summarized.

Patients will be assessed for AEs at all scheduled and unscheduled visits. Intermacs-defined AEs after HVAD implant will be summarized by severity, causal relationship to device, and outcome. The SAE, Serious Adverse Device Effect (SADE) and Unanticipated Serious Adverse Device Effect (USADE) will also be summarized. All AE incidence and rates (events per patient-year (EPPY)) will be summarized. Only events while a patient participated in Apogee will be included (12 month follow up visit, 365 days post implant, DT PAS exit, or withdrawal from Apogee).

The number and percentage of patients experiencing each specified AE using the Intermacs version 5 definitions, as well as number of events and event rate per patient-year will be summarized. All adverse events from induction of anesthesia until pump removal (with no replacement to another HVAD) will be summarized. If the device is turned off, but not removed, or if the device is repositioned, adverse events should be continued to be collected throughout follow-up.

The PSR MCS database underwent multiple changes to the AE forms throughout the lifecycle of the Apogee study. Cardiac arrhythmias, device malfunctions/failures, neurological dysfunctions, right heart failure, and other Intermacs AE categories will be reviewed by Medtronic Safety to reclassify the event to meet Intermacs Version 5.0 AE definitions as needed. Other events as needed will also be reviewed and reclassified. Detailed subcategory information (e.g., neurological dysfunction type) will be provided, as applicable and available. Reclassified events will be used in the summary tables if available; otherwise, the site entered data will be used. The AEs will be summarized using Intermacs V5.0 definitions.

Analyses will be done on the Safety Analysis Set.

The following subsets of the AEs will be summarized:

1. Intermacs V5 Adverse Events
2. Serious Adverse Events (SAE)
3. Adverse Device Effects (ADE)
4. Serious Adverse Device Effects (SADE)
5. Unanticipated Serious Adverse Device Effects (USADE)
6. Adverse Events Resulting in Death
7. Non-serious Adverse Events where frequency is greater than 5%

7.10 Safety Evaluation

7.10.1 Adverse Events

All study device and procedure related events, as well as reportable events, listed below, are required to be reported to Medtronic upon awareness. All AEs defined according to INTERMACS Manual of Operations Version 5.0 (See the PSR MCS base protocol with DT PAS and Apogee specific amendments) will be summarized.

- Arterial Non-Central Nervous System (CNS) Thromboembolism
- Cardiac Arrhythmias

- Device Malfunction/Failure
- Hemolysis
- Hepatic Dysfunction
- Hypertension
- Major Bleeding
- Major Infection
- Myocardial Infarction
- Neurological Dysfunction
- Pericardial Fluid Collection
- Psychiatric Episode
- Renal Dysfunction
- Respiratory Failure
- Right Heart Failure (RHF)
- Venous Thromboembolism
- Wound Dehiscence
- Other SAE

All AEs collected during the study post initial implant while the device is implanted in the body will be included in the tables. The tables will provide the number of patients who experienced an event, the number of events and the events per patient year. Tables for AEs, SAEs, SADEs, and USADEs will be summarized. Refer to section 7.9.5.2 for further detail.

The PSR MCS database underwent multiple changes to the AE forms throughout the lifecycle of the Apogee study. Cardiac arrhythmias, device malfunctions/.failures, neurological dysfunctions, right heart failure, and other Intermacs events will be reviewed by Medtronic Safety to reclassify the event to meet Version 5.0 of the Intermacs definitions as needed. Other events as needed will also be reviewed and reclassified. Detailed subcategory information (e.g., neurological dysfunction type) will be provided, as applicable and available. The AEs will be summarized using Intermacs V5.0 definitions. Only events while a patient participated in Apogee will be included (12 month follow up visit, 365 days post implant, DT PAS exit, or withdrawal from Apogee).

Analyses will be done on the Safety Analysis Set.

7.10.2 Deaths

Death information will be collected throughout the trial when the event occurs. Deaths will be gathered from the AE eCRF where the outcome='FATAL', or from the Exit eCRF, if not available on the AE form. Summary tables will be compiled showing the Intermacs category of the adverse event which led to death (see section 7.9.5.2), as well as the relationship of the AE to the procedure, system, and patient condition. The number and percent of patients will be provided. Only events while a patient participated in Apogee will be included (12 month follow up visit, 365 days post implant, exit from DT PAS, or withdrawal from Apogee).

7.10.3 Device Deficiencies

In the event a device deficiency occurs, the data will be collected on the eCRFs, as well as if the device deficiency could have led to an SAE. A listing will be compiled to summarize the device deficiency details, including a description of the deficiency, date of onset, actions taken as a result of the deficiency, and the outcome of the event. Only events while a patient participated in Apogee will be included (12 month follow up visit, 365 days post implant, exit from DT PAS, or withdrawal from Apogee).

7.10.4 Adverse Event Definitions/Classifications

All products enrolled in the PSR platform are approved with demonstrated evidence of safety and effectiveness for their intended use, at the time the study starts. Event definitions align with International Organization for Standardization standard 14155 (ISO 14155); however products followed in the PSR are approved, not investigational and the purpose of the PSR is not to demonstrate product safety and effectiveness for the purpose of obtaining product approval, new material, or design change for medical device already on the market. Table 5 provides additional details below.

Table 5: Adverse Event and Device Deficiency Definitions

Adverse Event (AE) (ISO 14155):	
Any untoward medical occurrence, unintended disease or injury, or untoward clinical signs (including abnormal laboratory findings) in subjects, users or other person, whether or not related to the investigational medical device and whether anticipated or unanticipated.
 
Note 1: This definition includes events related to the investigational medical device or the comparator.
 
Note 2: This definition includes events related to the procedure involved.
 
Note 3: For users or other persons, this definition is restricted to the investigational medical device.

Adverse Device Effect (ADE) (ISO 14155):	
Adverse event related to the use of an investigational medical device.

	
Note 1: This definition includes any adverse event resulting from insufficient or inadequate instructions for use or the deployment, implantation, installation, or operation, or any malfunction of the medical device.
 
Note 2: This definition includes any event resulting from user error or from intentional misuse of the medical device.

Serious Adverse Event (SAE) (ISO 14155):	
Adverse event that:
 
a) led to a deathb) serious deterioration in the health of the subject, users or other persons as defined by one or more of the following:
• a life-threatening illness or injury• a permanent impairment of a body structure or a body function including chronic disease• in-patient or prolonged hospitalization• medical or surgical intervention to prevent permanent impairment to body structure or a body functionc) led to foetal distress, foetal death or a congenital abnormality or birth defect including physical or mental impairment. 
Note: Planned hospitalization for a pre-existing condition or a procedure required by the CIP, without serious deterioration in health, is not considered a serious adverse event.

Serious Adverse Device Effect (SADE) (ISO 14155):	Adverse device effect that has resulted in any of the consequences characteristic of a serious adverse event.
Procedure-Related Adverse Event:	Adverse event that is related to the procedure of a device/system of interest.
Unanticipated Serious Adverse Device Effect (USADE) (ISO 14155):	Serious adverse device effect which by its nature, incidence, severity or outcome has not been identified in the current risk assessment.
Device Deficiency (DD) (ISO 14155):	
Inadequacy of a medical device with respect to its identity, durability, reliability, usability, safety or performance.
 
Note: Device deficiencies include malfunctions, use errors, and inadequacy in the information supplied by the manufacturer including labelling. This definition includes device deficiencies related to the investigational medical device or the comparator.

Pre-existing conditions (e.g. disease signs and/or symptoms) that, in the opinion of the responsible clinician, existed prior to registry participation are not considered reportable, unless the condition recurs after the patient has recovered from the pre-existing condition, or the condition worsens in intensity or frequency. Additionally, planned hospitalizations for a pre-existing condition without serious deterioration in health are not considered serious adverse events. An example of this includes prophylactic admissions to hospital for INR management.

